### **8.1.2 Primary analysis of the primary efficacy variable**

Seizure frequency will be analyzed using analysis of covariance (ANCOVA) with terms for treatment and center (pooled appropriately), on log-transformed seizure frequency using the transformation of  $\ln(X+1)$ , where X is the seizure frequency. Log transformed Baseline seizure frequency will be used as a covariate. Assumptions for the parametric model will be evaluated by diagnostic (eg, Shapiro-Wilk test for normality) and graphical methods such as residual plots, including normal probability plots, histograms, and plots of residuals versus Baseline covariate values and treatment. An assessment will be made with regards to the influence of individual observations (eg, extreme outliers) on the analysis. To the extent feasible, such potential influential observations will be identified prior to unblinding, and an assessment will be made with regard to the potential impact of such data, including the evaluation of alternative statistical methodology such as non-parametric methods. If deemed that a non-parametric method is warranted, an ANCOVA model on rank of seizure frequency per 28 days with terms for treatment and center (pooled appropriately) will be employed as the primary analysis. Ranked seizure frequency per 28 days during the Baseline Period will be used as a covariate.

The seizure frequency between treatment and placebo will be compared using the least squares means (LSMs). The percent reduction over placebo will be estimated as  $100 \times (1 - \exp[\text{LSM}_{\text{LCM}} - \text{LSM}_{\text{placebo}}])$ . A 95% CI will also be calculated for the percent reduction over placebo.

Partial-onset seizure frequency per 28 days during the Baseline Period and during the Maintenance Period, and the change from Baseline will be summarized by treatment group. This summary will be repeated by treatment group and age group, using the levels defined in section 4.8.

### **8.1.3 Secondary analyses of the primary efficacy variable**

The primary analysis of the primary efficacy variable described in section 8.1.2 will be repeated for the PPS.

### **8.1.4 Supportive and sensitivity analyses of the primary efficacy variable**

The impact of missing data on the primary efficacy analysis will be evaluated by repeating the primary analysis of the primary efficacy variable detailed in section 8.1.2 on observed cases.

For subjects who prematurely discontinue from the study, only data recorded up to their ETV will be used to obtain a partial-onset seizure frequency estimate for the Maintenance Period.

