13.6 Handling of dropouts or missing data

As described in Section 13.3, for subjects who discontinue prior to the Maintenance Period, all available seizure frequency data will be carried forward from the Titration Period for the Maintenance Period analysis. For subjects who prematurely discontinue during the Maintenance Period, all available seizure frequency data in the Maintenance Period will be carried forward for the entire Maintenance Period. Subjects who discontinue prior to any efficacy data collection will not be included in the analyses (ie, data will not be carried forward from Baseline). The imputation for the seizure frequency data will not carry forward into the Transition and Taper Periods.

The impact of missing data on the assessment of primary efficacy will be evaluated with sensitivity analyses with further details to be included in the SAP.

No imputation of missing values associated with an individual date or visit is planned for the primary safety analysis, with the exception of partial date information for AEs and concomitant medications in order to determine whether they are treatment emergent.

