#### Maintenance Period

The day after the end of the Titration Period (Visit 5) and prior to or on the end date of the Maintenance Period (Visit 8) for subjects who complete the Maintenance Period, or the day after the end of the Titration Period (Visit 5) and prior to or on the date of the ETV for subjects who

discontinue during the Maintenance Period. If a subject does not have a Visit 8/ETV, then either the date of the last scheduled or unscheduled visit during the Maintenance Period or the date of last known dose of study medication during the Maintenance Period, whichever is later, will define the end date of the Maintenance Period.

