### **4.2 Handling of dropouts or missing data**

#### **4.2.1 Missing data**

For subjects who discontinue prior to the Maintenance Period, all available seizure frequency data will be carried forward from the Titration Period for the Maintenance Period analysis. For subjects who prematurely discontinue during the Maintenance Period, all available seizure

frequency data in the Maintenance Period will be carried forward for the entire Maintenance Period.

Subjects who discontinue prior to any efficacy data collection will not be included in the analysis (ie, data will not be carried forward from Baseline). The imputation for the seizure frequency data will not carry forward into the Transition and Taper Periods.

No imputation of missing values associated with an individual date or visit is planned for the primary safety analysis, with the exception of partial date information for AEs and concomitant medications in order to determine whether the AEs are treatment-emergent or the medications are concomitant.

With respect to AEs, events with missing intensity will be assumed to be severe. Events with missing relationship to study medication per the investigator will be assumed to be related. Incomplete or missing dates for events will be handled as described in section 3.2.2.

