### **8.1 Statistical analysis of the primary efficacy variable**

#### **8.1.1 Derivations of primary efficacy variable**

The primary efficacy variable is the change in partial-onset seizure frequency per 28 days from Baseline to the Maintenance Period. Seizure frequency per 28 days will be based on the number of days for which seizure information was provided during the specified time interval.

Seizure frequency per 28 days will be calculated as  $([\text{number of seizures over the specified time interval}] \text{ divided by } [\text{number of days in the interval}])$  multiplied by 28.

The partial-onset seizure frequency per 28 days will be calculated for both the Baseline Period and for the Maintenance Period, and the change from Baseline calculated.

If a seizure cluster is reported, the highest recorded daily seizure frequency during the Treatment Period for the seizure type associated with the report of a seizure cluster will be used as the imputed seizure frequency for the day on which the cluster occurred.

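### The only missing-data sensitivity analysis returns the primary value for every Maintenance dropout and never varies the assumption about seizure frequency after dropout

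*SAP*

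**What the plan says.** Protocol 13.6 makes the commitment: the impact of missing data on primary efficacy "will be evaluated with sensitivity analyses with further details to be included in the SAP".

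The primary handling is set out in Protocol 13.6 and SAP 4.2.1. For a subject who leaves during Maintenance, "all available seizure frequency data in the Maintenance Period will be carried forward for the entire Maintenance Period". For a subject who leaves before Maintenance, "all available seizure frequency data will be carried forward from the Titration Period for the Maintenance Period analysis".

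Two definitions fix what the carried-forward number is. SAP 8.1.1: "Seizure frequency per 28 days will be based on the number of days for which seizure information was provided during the specified time interval". SAP 3.2.2 sets the Maintenance interval of a Maintenance dropout as "the day after the end of the Titration Period (Visit 5) and prior to or on the date of the ETV".

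SAP 8.1.4 then evaluates missing data by "repeating the primary analysis of the primary efficacy variable detailed in section 8.1.2 on observed cases", and adds that for subjects who discontinue, "only data recorded up to their ETV will be used to obtain a partial-onset seizure frequency estimate for the Maintenance Period". No second missing-data analysis is specified. The Per Protocol Set repeat in SAP 8.1.3 is there, according to SAP 4.6, to examine important protocol deviations. SAP 3.9 declares no changes to the analyses in the protocol.

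**The concern.** A missing-data sensitivity analysis is useful only if it replaces the untestable assumption of the primary analysis with a different one. Here that assumption is that a discontinuing subject would have kept the seizure frequency recorded while still in the study. If the sensitivity analysis rests on the same assumption, agreement between the two follows from the derivation and is not evidence.

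This matters because several routes out of the trial plausibly depend on tolerability or response. Subjects who will not reach the minimum target dose leave during Titration (Protocol 5.1, 7.2.1). Those who need a dose change leave during Maintenance (Protocol 7.2.2, 8.3). Intolerable adverse events and any needed change in AED daily dose are withdrawal criteria throughout (Protocol 6.3). A clinical study report that cites close agreement between the primary and the observed-case result as robustness would be claiming something the analysis had not tested.

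**Working it through.** **1. Maintenance dropouts.** Take s partial-onset seizures in d diary days between the day after Visit 5 and the ETV.
- Observed-case value (SAP 8.1.4 with 8.1.1): (s/d) × 28 = 28s/d.
- Primary value, rate carried over the planned 70 days: [(s/d) × 70] / 70 × 28 = 28s/d.
- Example: 6 seizures in 21 days gives 8.0 per 28 days in both.

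The values agree for any s and d. The 10% diary-completeness rule in SAP 4.2.5 is not limited to one of the two analyses, so it does not separate them.

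**2. Titration dropouts.** SAP 8.1.4 allows two readings.
- They keep their data up to the ETV. SAP 3.2.2 ends their Titration Period at the ETV, so this is the Titration rate that the primary already uses. The two analyses then coincide for all subjects.
- They are excluded because they have no Maintenance data. The estimate can then move, but only because subjects are deleted.

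**3. How far the exclusion reading can move the estimate.** This was simulated with 154 per arm, 400 runs per setting and a residual SD of 0.73. The baseline distribution, the Titration values (including a weaker LCM effect in Titration) and the Titration share of dropouts are assumptions, because the documents give none of them.
- 0% of dropouts in Titration: difference 0.0000 in every run, as step 1 requires.
- 25% to 100% in Titration: mean absolute difference per run of 0.015 to 0.034 on the log scale at 14% dropout, and 0.022 to 0.050 at 24%.

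**4. The plan's own sample size.** Inputs from Protocol 13.8 and SAP 2.4: difference -0.249, SD 0.73, two-sided 5%, 80% power. Power = Φ(|effect| / (0.73 × √(2/n)) − 1.96). At n = 135 this is Φ(0.249/0.0889 − 1.96) = 80.0%, so the stated 135 per arm reproduces. The stated 154 is 135 × 1.14. The reduction is 1 − exp(−0.249) = 22.0%.

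**5. An illustration of what goes untested.** Suppose a fraction p of the LCM arm discontinues before the end of Maintenance and none of those subjects has any Maintenance benefit, with placebo and the SD unchanged. The effect is then −0.249 × (1 − p).

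| Scenario | n per arm | Effect | Reduction | Power |
|---|---|---|---|---|
| No dilution | 154 | -0.249 | 22.0% | Φ(0.249/0.0832 − 1.96) ≈ 85% |
| p = 14% | 154 | -0.214 | 19.3% | Φ(0.2141/0.0832 − 1.96) ≈ 73% |
| p = 24% | 154 | -0.189 | 17.2% | Φ(0.1892/0.0832 − 1.96) ≈ 62% |
| p = 24%, enrolment raised | 167 (135 × 1.24) | -0.189 | 17.2% | about 66% |
| p = 24%, enrolment raised | 178 (135 / 0.76) | -0.189 | 17.2% | about 69% |

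The 24% is the cap in Protocol 13.7 and SAP 2.4.1. If all dropout fell in Maintenance, the observed-case run would differ from the primary by exactly zero in every row.

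**The case against.** The best defence is that observed-case analysis conventionally leaves out subjects with no data in the period. On that reading Titration dropouts leave the model, whereas the primary includes them with Titration data. The rerun then checks one real step, and it does so for the subjects who could not reach the target dose. This stands. A reader might infer that SAP 8.1.4 cannot show any effect of missing data; the documents do not support that, because the exclusion reading is open and step 3 shows that the estimate can move under it. For the same reason, one cannot say that agreement is mostly built in: the split of dropouts between Titration and Maintenance is not given.

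A reader might also pair the diluted effect with 135 per arm and quote power of about 67% and 57%. That counts dropout twice. Subjects with post-Baseline seizure data stay in the Full Analysis Set (SAP 3.5.2) and are carried forward, so about 154 per arm are analysed. SAP 2.4.1 would also raise enrolment if dropout exceeded 14%.

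Nor do the documents show that dropout will differ between arms. That is an inference from the withdrawal rules.

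Finally, Protocol 13.6 names no method, so the sponsor was free to choose one. That is true, but the choice should still vary the assumption in question, and this one does not.

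**Conclusion.** The point holds in limited form. SAP 8.1.4 is uninformative about the unobserved time of Maintenance dropouts, and this follows exactly from the plan's definitions. It is ambiguous for Titration dropouts. On neither reading does the plan examine a departure from the carry-forward assumption, so agreement with the primary must not be presented as robustness for Maintenance dropouts. The primary analysis itself is not invalidated.

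The figures in step 5 are an illustrative upper bound for loss of benefit, not a forecast. They assume that every LCM discontinuer loses the whole benefit, although Maintenance dropouts contribute real on-treatment days. They assume that all dropout falls before the end of Maintenance, although the documents speak of an overall study rate that may include later leavers with complete Maintenance data. They also apply that overall rate to the LCM arm. They cover Titration and Maintenance dropouts together, so they do not isolate the gap for Maintenance dropouts alone.

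**What to change.** In SAP 8.1.4:
- Keep the observed-case ANCOVA, labelled as descriptive.
- State whether Titration dropouts are excluded from it or keep their data up to the ETV.
- Add a sensitivity analysis that varies the post-dropout assumption for the unobserved Maintenance days only, retaining the Maintenance diary data that were observed. One suitable choice is placebo-reference multiple imputation, with a delta-adjusted tipping point for LCM discontinuers. Imputing the whole Maintenance value from Baseline would discard nearly all the diary data of a subject who leaves late in the 70 days.

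The cost is SAP wording and modest programming, settled before unblinding. Data collection, the primary analysis and the sample size do not change. The sponsor must accept that the sensitivity estimate may be less favourable than the primary.

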## **8.2 Statistical analysis of the secondary efficacy variables**

The secondary efficacy variables will be summarized and/or analyzed for the FAS.

### **8.2.1 Change in partial-onset seizure frequency per 28 days from Baseline to entire Treatment Period**

The partial-onset seizure frequency per 28 days will be calculated for both the Baseline Period and for the entire Treatment Period, as detailed in section 8.1.1. The change from Baseline will also be calculated.

The change in partial-onset seizure frequency per 28 days from Baseline to the entire Treatment Period will be analyzed as detailed in section 8.1.2.

Partial-onset seizure frequency per 28 days during the Baseline Period and during the entire Treatment Period, and change from Baseline will be summarized by treatment group. This summary will be repeated by treatment group and age group, using the levels defined in section 4.8.

The change in seizure frequency per 28 days from Baseline to the Treatment Period, defined as the combined Titration and Maintenance Periods, will be summarized by treatment group (LCM or placebo) using descriptive statistics. Statistical testing will be performed using an ANCOVA model with terms for treatment and pooled site and baseline seizure frequency as a covariate.

The change in seizure frequency by period will also be summarized using descriptive statistics by treatment group and seizure type.

The change in seizure frequency by visit will also be summarized, based on observed analysis. For each visit during the Titration Period, the LCM treatment group will be compared to placebo in an exploratory onset of efficacy analysis. Statistical testing will be performed using an ANCOVA model with terms for treatment and pooled site and baseline seizure frequency as a covariate using data recorded at each individual Titration Period visit.

### **8.2.2 Proportion of responders, where a responder is a subject experiencing a 50% or greater reduction in partial-onset seizure frequency from Baseline to end of Maintenance Period**

The secondary efficacy variable is the proportion of responders, where a responder is a subject experiencing a 50% or greater reduction in partial-onset seizure frequency from Baseline to the end of Maintenance Period.

Percent reduction will be calculated as  $([\text{absolute reduction in partial-onset seizure frequency}] \div [\text{Baseline partial-onset seizure frequency}]) \times 100$ .

Absolute reduction in partial-onset seizure frequency is calculated as  $(\text{Baseline partial-onset seizure frequency}) - (\text{Maintenance Period partial-onset seizure frequency})$ .

The subject is considered a responder if the data shows a 50% or greater reduction in partial-onset seizure frequency from Baseline to end of Maintenance Period, otherwise the subject will be considered a non-responder.

This variable will be analyzed using a logistic regression model with terms for treatment and center to measure the association between the response variable and treatment after controlling for center. The odds ratio, 95% CI, and p-value associated with treatment will be presented.

The number and percentage of responders will be summarized by treatment group.

The response to treatment for each response level will also be summarized using descriptive statistics by treatment group and seizure type, with the seizure types presented as follows: simple partial seizures (IA), complex partial seizures (IB), partial seizures evolving to secondarily generalized (IC), generalized seizures (II), and unclassified epileptic seizures (III). This summary will be repeated by treatment group and age group, using the levels defined in section 4.8.

Only subjects who experienced the respective seizure type during the Baseline Period will be included in the analysis for that seizure type with only the seizure frequencies of that seizure type being used in the analysis. Subjects can be analyzed under multiple seizure types in these summaries. No statistical testing will be performed for these by seizure type summaries.

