6.3 Withdrawal criteria

Subjects are free to withdraw from the study at any time, without prejudice to their continued care.

Subjects **must** be withdrawn from this study if any of the following events occur:

1. Subject experiences intolerable AEs, including clinically relevant abnormal laboratory findings that, in the opinion of the investigator, preclude further participation in the study.
2. The sponsor or a regulatory agency requests withdrawal of the subject.
3. Subject has QTc interval ≥ 500 ms that is confirmed by a cardiologist overread on any ECG.
4. Subject develops a second degree atrioventricular (AV) block while awake or develops a third degree AV block.
5. For subjects ≥ 6 years of age, subject has actual suicidal ideation since last visit as indicated by a positive response ("Yes") to either Question 4 or Question 5 of the C-SSRS. The subject should be referred immediately to a Mental Healthcare Professional and must be withdrawn from the study.

6. Subject is unwilling or unable to continue, or the parent/legal representative is unwilling or unable to allow the subject to continue in the study.
7. Investigator decides that withdrawal from further participation would be in the subject's best interest.
8. Subject experiences convulsive status epilepticus.
9. Subject uses rescue medication in excess of that permitted by the protocol.
10. In the case of liver function test (LFT) results of transaminases (AST, ALT, or both) $\geq 3x$ ULN to $< 5x$ ULN and total bilirubin $\geq 2x$ ULN or transaminases (AST, ALT, or both) $\geq 5x$ ULN, the study medication must be immediately discontinued and the subject withdrawn from the study. The LFTs will be repeated as soon as possible, and in no case > 1 week later.
11. Female subject who achieves menarche and does not practice contraception as provided in Exclusion Criteria 6 unless sexually abstinent. Subject becomes pregnant, as evidenced by a positive pregnancy test.
12. Subject needs any alteration in AED daily dose or VNS settings.

Participation in this study may be discontinued for any of the following reasons:

1. Subject has any clinically relevant change in medical or psychiatric condition (if in the opinion of the investigator, the change in condition warrants discontinuation from the study).
2. Subject requires a medication that is not permitted by the protocol.
3. Subject and/or delegated caregiver is noncompliant with study procedures or medication, in the opinion of the investigator.

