## **8 EFFICACY ANALYSES**

The primary and secondary efficacy variables will be measured using data obtained from the subject diary. Subjects or parents/caregivers will keep a diary to record the daily seizure activity from the beginning of the Baseline Period until the last visit, recording both seizure type, seizure frequency, and whether the seizures were a cluster.

Each seizure code in the clinical database will be mapped to exactly 1 of the ILAE seizure codes based on the 1981 ILAE classification (Seizure Count eCRF).

The assessment of efficacy is based on seizure frequency, and will be analyzed primarily for the FAS. All CIs presented will be 95% 2-sided CIs.

For subjects who prematurely discontinue from the study, last observation carried forward method as described in section 4.2 will be applied to obtain a seizure frequency estimate for the Maintenance Period.

All efficacy variables will be listed.

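### The 50% responder definition lets an early-withdrawn subject count as a responder to the end of Maintenance on a short carried-forward window, and no sensitivity analysis of that variable would show it

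*SAP*

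**What the plan says.** SAP 8.2.2 compares Baseline with Maintenance frequency and sets one condition: "The subject is considered a responder if the data shows a 50% or greater reduction". Everyone else is a non-responder. Neither completing Maintenance nor the reason for leaving enters the definition.

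For subjects who leave early, SAP 8 says "last observation carried forward method as described in section 4.2 will be applied to obtain a seizure frequency estimate for the Maintenance Period". SAP 4.2.1 gives two cases. A subject who leaves before Maintenance has "data will be carried forward from the Titration Period for the Maintenance Period analysis". For one who leaves during Maintenance, "data in the Maintenance Period will be carried forward for the entire Maintenance Period". SAP 3.2.2 closes the observed Maintenance interval "prior to or on the date of the ETV for subjects who" discontinue. No minimum length is set.

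Protocol 6.3 makes withdrawal mandatory for, among others, criterion 8 ("Subject experiences convulsive status epilepticus") and criterion 9 ("Subject uses rescue medication in excess of that permitted by the protocol"). Criterion 12 does the same for a required change to the daily dose of a background AED or to VNS settings.

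The responder proportion is the first-listed secondary variable. It is tested by logistic regression with an odds ratio and p-value (SAP 8.2.2), and it has its own power statement (SAP 2.4). The per-protocol and observed-case analyses (SAP 8.1.3 and 8.1.4) are specified for the primary variable only.

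**The concern.** Two of the mandatory withdrawal reasons, status epilepticus and excess rescue use, are naturally read as loss of seizure control. The responder rule cannot see them. What counts is the average frequency up to the Early Termination Visit, and that average can be low when a subject did well and then had one serious event. A subject who stopped in Titration can likewise be a Maintenance responder without a single Maintenance day.

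A short window is also noisier than the full 10 weeks, so chance alone more often produces a 50% fall. Two neighbouring variables are conditioned: seizure-free days on entering Maintenance (SAP 8.2.8) and seizure-free status on completing it (SAP 8.2.9). The tested responder variable has no such condition. At stake is how far its odds ratio reflects response sustained over 10 weeks.

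**Working it through.** **The plan's own figure.** SAP 2.4 gives responder rates of 22% and 40%, 135 per arm and a two-sided 5% continuity-corrected chi-square test. Power is Φ[(|p1−p2| − 1/n − 1.96·√(2p̄(1−p̄)/n)) / √((p1(1−p1)+p2(1−p2))/n)]. With p̄ = 0.31: (0.18 − 0.0074 − 0.1103)/0.0552 = 1.13, so power is 0.870. The stated 87% is reproduced.

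**Single subjects.** Frequency is count × 28 / observed days (SAP 8.1.1).
- Take a Baseline of 4 per 28 days, 20 seizure-free Maintenance days, then status epilepticus counted as one seizure on day 21, with the Early Termination Visit that day. Frequency is 1 × 28/21 = 1.33 and the reduction is 1 − 1.33/4 = 67%: a responder. Two counted seizures would give 2.67 and a 33% reduction: not a responder.
- Take the same Baseline, withdrawal after 14 Titration days and one seizure. Frequency is 1 × 28/14 = 2 and the reduction is 50%: a Maintenance responder who never entered Maintenance.

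**Chance response by window.** From the documents: Baseline is a count over 56 days with at least 2 seizures required (Protocol 6.1, criterion 6), and full Maintenance is 70 days. Assumed, because the documents give no values: Baseline frequency, dispersion and an unchanged true rate. Each cell is simulated with 400,000 draws. A subject responds if the 28-day rate in the window is at most half the Baseline rate.

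| Baseline per 28 days | 14 days | 28 days | 70 days | Ratio, 14 to 70 | Ratio if variance = 3 × mean |
|---|---|---|---|---|---|
| 2 | 38.8% | 32.1% | 18.3% | 2.1 | 1.7 |
| 4 | 28.7% | 19.3% | 8.2% | 3.5 | 2.1 |
| 8 | 17.7% | 9.1% | 2.3% | about 8 | 2.8 |

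With overdispersed counts the ratios fall but the absolute gap does not. At Baseline 4 it is 45.6% − 22.0% = 23.6 points, against 28.7% − 8.2% = 20.5 points for Poisson.

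If the window must contain at least one counted seizure (Poisson), 14 v 70 days becomes 3.2% v 17.7% at Baseline 2, 17.5% v 8.2% at Baseline 4 and 16.1% v 2.3% at Baseline 8. The direction reverses at Baseline 2 and holds at 4 and 8.

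**Within an arm.** With 14% dropout and a 20% to 40% chance that a leaver is scored a responder, 154 × 0.14 × 0.20 = 4.3 to 154 × 0.14 × 0.40 = 8.6 subjects are affected, or 2.8 to 5.6 points of the arm's rate.

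**Between arms (illustration only).** Assume Baseline 4, 14 observed days for every leaver, no drug effect, and dropout of 18% on LCM and 10% on placebo. The difference is (0.18 − 0.10) × (0.287 − 0.082) = 1.6 points towards LCM. Reversing the split gives 1.6 points towards placebo. Scoring leavers as non-responders under the first split gives 0.82 × 0.082 − 0.90 × 0.082 = −0.7 points.

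**Power of the proposed rerun.** Assume 22% and 40% apply to completers and 14% leave each arm. The rates become 0.22 × 0.86 = 18.9% and 0.40 × 0.86 = 34.4%. With 154 per arm: (0.1548 − 0.0065 − 0.0988)/0.0496 = 1.00, so power is 84%. If 10% leave placebo and 18% leave LCM, the rates are 19.8% and 32.8% and power is 69%. At 24% in both arms it is 77%.

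**The case against.** The strongest reply is that the window runs to the Early Termination Visit, so a counted seizure that triggers withdrawal falls inside it. One seizure in 7 days is already 4 per 28 days, so Baseline would have to be at least 8 for that subject to qualify. This stands. For withdrawals caused by worsening, the short window need not inflate response and can do the opposite at low Baseline frequency.

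A reader might infer that the rule multiplies chance response several-fold throughout. The documents do not support that. The ratio is about 2 at Baseline 2, and overdispersion lowers it everywhere. A quick Poisson sum that treats Baseline as known exactly gives 41% v 7% at Baseline 4, but Baseline is itself a 56-day count, and allowing for that gives 29% v 8%.

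A reader might also infer that LCM gains, because titration to tolerability could cause more LCM withdrawals. Withdrawals for worsening could equally be commoner on placebo. The documents give no split, timing or reasons.

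Nor does every withdrawal under criterion 12 mark a treatment failure. A change in AED dose need not mean worsening, so making it an automatic non-response would be a debatable choice of estimand.

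The missing-diary rule (SAP 4.2.5) is a possible safeguard: a subject with more than 10% of entries missing in an interval is left out. Applied to the planned 70 days it would remove most leavers, but it would also defeat the carry-forward rule. Applied to the interval ending at the Early Termination Visit it leaves them in. The SAP does not say which, and the second reading fits SAP 3.2.2 and 4.2.1 better.

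Finally, this is a secondary variable without multiplicity adjustment (SAP 4.5), and disposition by reason and period is already planned (SAP 5.1). That limits the consequence, but it does not link responder status to withdrawal.

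**Conclusion.** The gap in the definition is real and needs no simulation: as written, a subject withdrawn for status epilepticus or excess rescue use, or never in Maintenance, can be a responder to the end of Maintenance, and no planned analysis of this variable would reveal it. The observed-case analysis would not help even if extended to this variable for Maintenance dropouts, because their observed and carried-forward frequencies are the same.

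The size is conditional. The chance rates rest on assumed Baseline frequencies, Poisson counts and no change in rate. The 1.6-point between-arm figure also rests on an assumed split and 14 observed days, has no fixed sign, and is small beside the planned 18-point difference (40% minus 22%). The documents do not support a claim that the responder result is biased towards LCM. This is an inexpensive improvement to make before unblinding, not a flaw that undermines the trial.

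**What to change.** In SAP 8.2.2, add a prespecified sensitivity analysis that repeats the logistic model with every FAS subject who did not complete Maintenance scored as a non-responder. Add a table of responders by treatment, Maintenance completion and reason for withdrawal. The main responder analysis and the withdrawal criteria in Protocol 6.3 stay as they are.

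The cost is a short SAP insertion, one rerun of an existing model and one table, with no new data. Responder rates in that analysis will be lower, and so will its power where LCM dropout is not below placebo dropout: about 84% with balanced 14% dropout and about 69% with 10% placebo and 18% LCM, under the assumptions above. It penalises the arm with more dropouts, so it should be read beside the main analysis as a bound, not as an unbiased replacement.
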